## Background

Antifibrinolytic medications such as tranexamic acid (TXA) have been shown to reduce blood loss and transfusion requirement in trauma and surgical patients across numerous sub-specialties[1]. In trauma surgery, a large multi-center randomized controlled trial (CRASH-2) demonstrated reduced risk of death from bleeding and all-cause mortality with early, continuous use upon presentation to a trauma center[2, 3]. In orthopedic surgery, TXA is well studied for use in elective hip and knee replacement as well as spine surgery [4-6]. At Mayo Clinic Rochester, the routine administration of tranexamic acid has become part of the typical protocol for elective hip and knee replacement as well as major spinal procedures. The use of TXA in orthopedic trauma patients is an area of current research interest. A 2010 prospective randomized, controlled trial of perioperative TXA demonstrated reduction in transfusion requirements for intertrochanteric hip fractures treated with short, cephalomedullary nails. This was clinically, though not statistically, significant [7]. We recently conducted a randomized, controlled trial at this institution to evaluated the use of TXA in patients with femoral neck fractures treated with hemiarthroplasty or total hip arthroplasty and found clinically, albeit not statistically, significant reduction in transfusion requirement[8]. Perhaps tempering the effect seen with perioperative administration of TXA is the blood loss that occurs prior to surgery, the so-called “hidden” blood loss that can be as substantial as 1/3 of total blood loss from a

hip fracture [7, 9]. This raises the question whether administration of tranexamic acid at the time of initial presentation after fracture could improve the perioperative care of these patients by decreasing the proportion of patients requiring transfusion and decreasing total blood loss. This would have potential implications for infection, morbidity and all-cause mortality from such fractures.

Recent literature has substantiated the safety of TXA administration in this fragile hip fracture patient population. A prospective, randomized trial assessing perioperative TXA administration for extracapsular hip fractures treated with cephalomedullary nails published in 2018 demonstrated reduction in blood loss and 20% reduction in transfusion rate without any increase in thrombotic complications[10]. Additionally, the protocol for bolus and subsequent infusion dosing of TXA initially recommended in the CRASH-2 trial has been validated with a recently published literature review evaluating the use of TXA in the pre-hospital setting to limit hemorrhage. They determined that the risk for vascular events was not increased due to drug administration above and beyond the anticipated increased risk due to the insult of trauma and hypovolemia secondary to blood loss. They concluded that this medication and dosing was safe for use even outside of the hospital setting[11].

## Methods

A single-center, prospective randomized study is proposed. Consecutive patients presenting with intertrochanteric hip fractures will be treated with tranexamic acid. Treatment will be initiated in the emergency department according to a previously studied protocol for trauma patients.

### Inclusion criteria

- AO/OTA fracture classification 31A
- Surgically treated with sliding hip screw or cephalomedullary nail (short or long)
- Low energy, isolated injury

-Age greater than 18 years old

**Exclusion Criteria**

-Intracapsular hip fractures: AO/OTA fracture classification 31B-C

-Polytrauma patients

-Creatinine clearance less than 30 mL/min

-History of unprovoked VTE and/or recurrent VTE

-Known history of Factor V Leiden, protein C/S deficiency, prothrombin gene mutation, anti-thrombin deficiency, anti-phospholipid antibody syndrome, lupus anticoagulant

-Pregnancy or breastfeeding (pregnancy tests will be performed on all patients of child-bearing potential)

-History of CVA, MI, or VTE within the previous 30 days

-Coronary stent placement within the previous 6 months

-Disseminated intravascular coagulation

-Intracranial hemorrhage

**Initial Patient Encounter**

The Orthopedic Trauma Service (OTS) in the emergency department will perform a history and physical exam. Hip radiographs will be obtained to evaluate fracture type and indicated operative procedure. If study criteria are met, informed consent will be obtained either from the patient or legally authorized representative. After consent is obtained, treatment will be initiated in the emergency room with study medication obtained by ED pharmacy.

TXA will be administered intravenously via bolus dose of 1g over ten minutes and an additional 1g over the subsequent 8 hours, in accordance with a previously studied protocol utilized in the CRASH-2 trial [2, 3]. Patients in the control group will receive a placebo medication in the ED. Neither group will receive perioperative bolus dosing of TXA.

### Operative Course

Prior to surgery, patients will undergo pre-anesthesia medical clearance and stabilization in coordination with the hospitalist medicine team. Anesthetic type (regional vs. general) will be at the discretion of our anesthesia colleagues.

During surgery, crystalloid maintenance fluids will be administered at a rate of 1.5 cc/kg/hour. Blood losses will be replaced with crystalloid solution in a 3:1 ratio, 5% albumin in a 1:1 ratio, or a combination. Changes of 20% in baseline heart rate or blood pressure which are felt to be due to hypovolemia will be managed with boluses of 10 cc/kg crystalloid solution or 500 cc of 5% albumin. Intraoperative transfusions will be given for hemoglobin levels less than 8 g/dL. If transfused, one unit of packed red blood cells will be administered at a time, with reassessment after each unit. Transfusion triggers will not apply to patients with active myocardial ischemia or hemorrhagic shock.

Surgical management will include either sliding hip screw or cephalomedullary nailing as clinically indicated, performed in routine fashion. Hemostasis will be attained prior to wound closure.

### Hospital Course

While admitted to the hospital, all patients will be co-managed between the orthopedic trauma service and the hospitalist medicine service. Hemoglobin levels will be checked daily through postoperative day three, and as indicated thereafter. Conservative triggers for blood transfusion will be used for all patients.

Transfusion will be considered for all patients with hemoglobin values of less than 8 g/dL with persistent symptoms or history of significant cardiac disease that may render the patient less able to compensate for significant anemia. Blood transfusion will be considered in all patients with hemoglobin less than 7 g/dL, regardless of symptoms. Hemoglobin triggers will not apply to patients with active myocardial ischemia or hemorrhage. When the decision is made to transfuse, one unit of packed red blood cells will be administered at a time, with reassessment after each unit.

All patients will receive standardized DVT prophylaxis including lower extremity sequential compression devices and low-molecular weight heparin, unless medically contraindicated or full therapeutic anticoagulation is required. Postoperative mobilization will begin as soon as clinically indicated.

Each hospital day, patients will be clinically evaluated for signs of symptomatic venous thromboembolic event (VTE), myocardial infarction (MI), cerebrovascular accident (CVA), and wound complications. Diagnostic workup will be performed only in the setting of acute symptoms. There will be no routine or mandatory screening with the exception of daily clinical evaluation by a member of the OTS trauma team as well as the hospitalist medicine team. VTE will be defined as symptomatic deep venous thrombosis diagnosed by duplex ultrasound, or pulmonary embolism diagnosed by contrast spiral chest CT or ventilation-perfusion scan. MI will be diagnosed using electrocardiogram and serial serum cardiac enzymes. CVA will be defined as transient ischemic attack or stroke diagnosed by head CT or MRI. Wound complications will include hematoma formation, dehiscence, and deep or superficial infection.

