#### Clinical Follow-up

Patient follow-up and disposition will be at the discretion of the treating surgeon. For the purposes of this study, patients will be followed for a period of six months from the day of surgery. At the time of follow-up, patients will be assessed for the incidence of complication including VTE, MI, CVA, wound complication, and all-cause mortality. If patients are not able to return to clinic, they (or their legally authorized representative) will be contacted by phone.

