#### Secondary Outcomes

-Mean number of units transfused per patient

-Calculated blood loss

-Incidence of symptomatic VTE diagnosed within 6 months of surgery

- Wound complications diagnosed within 6 months of surgery
- MI diagnosed within 6 months of surgery
- CVA diagnosed within 6 months of surgery
- All-cause mortality at 6 months

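### A PE, MI or stroke that kills before the named test is done meets no outcome definition and is counted only in all-cause mortality

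*Combined protocol and SAP*

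**What the plan says.** All places are in the combined protocol and SAP.

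- **Hospital Course, definitions.** "VTE will be defined as symptomatic deep venous thrombosis diagnosed by duplex ultrasound", or "pulmonary embolism diagnosed by contrast spiral chest CT or ventilation-perfusion scan". For the arterial outcomes: "MI will be diagnosed using electrocardiogram and serial serum cardiac enzymes" and "CVA will be defined as transient ischemic attack or stroke diagnosed by head CT or MRI".
- **Hospital Course, timing of tests.** "Diagnostic workup will be performed only in the setting of acute symptoms". There is no routine screening beyond daily clinical evaluation.
- **Clinical Follow-up.** "patients will be followed for a period of six months from the day of surgery", and at follow-up "patients will be assessed for the incidence of complication including VTE, MI, CVA, wound complication, and all-cause mortality". A phone call to the patient or a representative may replace a clinic visit.
- **Secondary Outcomes.** VTE, MI and CVA within six months are listed. Death is listed once, as "All-cause mortality at 6 months".
- **Analysis.** The six-month adverse events refer back to the earlier definitions. They are compared by chi-square test and logistic regression if follow-up is complete. If follow-up varies because of withdrawal or non-response, Kaplan-Meier and Cox methods are used. How a death enters the VTE, MI and CVA analyses is not stated.

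The visible text has no step for classifying a death by cause, no use of autopsy, death certificate or terminal record, and no category for a fatal or probable event.

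**The concern.** Thrombosis is the drug risk that the protocol itself takes up: the Background argues vascular safety, and the Exclusion Criteria remove patients with relevant thrombotic history. Sudden death is one of the most severe ways in which such an event can present, and it leaves no time for a test. Most of a six-month window is likely to fall after discharge, where a death may be learned of only by phone.

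If the written rule is followed, even an autopsy-proven PE in a patient who was never scanned is not a VTE. The reported absolute risks of VTE, MI and CVA would then be too low. Someone reading the safety tables could not tell how many deaths were probably thrombotic.

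**Working it through.** **1. What the definitions admit.** Three cases, read against Hospital Course and Secondary Outcomes:

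| Case | VTE, MI or CVA outcome | All-cause mortality |
|---|---|---|
| Named test positive, patient survives | counted | no |
| Named test positive, patient then dies | counted | counted |
| Fatal before the named test, cause documented or not | no definition met | counted |

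Only the third row is affected.

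**2. The plan's own figure.** The only design calculation is for transfusion: 50% versus 25%, two-sided α = 0.05, 80% power. With pooled variance,

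n = [1.960·√(2·0.375·0.625) + 0.842·√(0.5·0.5 + 0.25·0.75)]² / 0.25² = 57.7, so 58 per group, as stated.

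Nothing in it depends on thrombotic events or deaths, so no stated figure changes. The 78 per group used below is the enrolment target in Sample Size.

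**3. Possible number of uncounted events.** The documents give no rates. The following are assumptions: six-month mortality 10–20%, of which 10–25% thrombotic and untested; tested VTE, MI or CVA in 5–8% of patients.

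- Uncounted per arm: 78 × 0.10 × 0.10 = 0.8, up to 78 × 0.20 × 0.25 = 3.9.
- Tested per arm: 78 × 0.05 = 3.9, up to 78 × 0.08 = 6.2.
- Uncounted share of all thrombotic events: 0.78/(0.78 + 6.24) = 11%, up to 3.9/(3.9 + 3.9) = 50%. The upper end needs the highest mortality, the highest untested share and the lowest tested rate together.

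**4. Effect on the comparison.** Assume true risks of 5% (control) and 10% (TXA), 78 per arm. Observed risk = true risk × (1 − untested fatal share). Power is for the two-sided 0.05 test of two proportions.

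| Untested fatal share, control / TXA | Expected events | Risk difference | Risk ratio | Power |
|---|---|---|---|---|
| 0 / 0 | 3.9 v 7.8 | 5.0 points | 2.0 | 22% |
| 10% / 10% | 3.5 v 7.0 | 4.5 points | 2.0 | 20% |
| 30% / 30% | 2.7 v 5.5 | 3.5 points | 2.0 | 16% |
| 10% / 30% | 3.5 v 5.5 | 2.5 points | 1.56 | 10% |

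With equal shares the factor (1 − share) cancels from the risk ratio. With unequal shares it does not, and the distortion can go either way. Reversing the last row (30% control, 10% TXA) gives 0.09/0.035 = 2.57 and a difference of 5.5 points. With true risks of 8% and 10%, shares of 10% and 30% move the ratio from 1.25 to 0.07/0.072 = 0.97.

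**5. The time-to-event fallback.** If deaths are censored, 1 − Kaplan-Meier estimates the risk as though nobody died. Assume a net risk of 8%, mortality of 20% and constant hazards:

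- h = −ln 0.92 = 0.0834; d = −ln 0.80 = 0.2231.
- Cumulative incidence = h/(h + d) × (1 − e^−(h+d)) = 0.272 × 0.264 = 7.2%, against 8% from Kaplan-Meier.

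The gap of 0.8 points is about 0.6 patients in 78. It overstates incidence, so it runs opposite to the under-count in steps 3 and 4.

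**The case against.** Symptomatic, test-confirmed events are a specific and legitimate outcome definition. The trial is placebo-controlled, and clinicians and data collectors are blinded, so the detection rules are the same in both arms. Every death is still compared between arms in all-cause mortality, with no attribution error. These are secondary outcomes with little power in any case (about 22% in the illustration). Without planned autopsies, many sudden deaths would end up as undetermined.

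Most of this stands, and it limits the point. Three stronger readings are tempting and are not supported:

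- *All fatal thrombotic events are lost, or the definitions require a living patient.* The text says neither. An event confirmed by its test before death counts.
- *The thrombotic comparison is biased toward no harm.* Equal under-capture leaves the risk ratio alone. A distorted ratio needs an untested fatal share that differs by arm, and nothing in the documents shows that it would.
- *Cause of death is not collected at all.* The case form is not among the documents, and some text was removed before review, so silence cannot settle this. Likewise, it is an inference that a patient who dies would be scored event-free under the chi-square route; the Analysis section does not say.

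What the objection does not remove is the third row of the table in step 1. A documented fatal PE, MI or stroke without the named test has no place in its own outcome. Leaving staff to make exceptions case by case would invite inconsistent scoring.

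**Conclusion.** The point holds in a limited form. Fatal thrombotic events not confirmed by the named test before death fall outside VTE, MI and CVA for the whole six months and appear only as deaths. Absolute thrombotic risk is under-counted. With equal untested shares, the risk difference and power also shrink while the risk ratio stays the same.

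The size cannot be derived from the documents. The range of 0.8 to 3.9 uncounted events per arm rests wholly on assumed mortality and an assumed untested share. The primary outcome and the sample size are unaffected. This is a low-cost improvement to the accuracy of the safety results; it does not make those comparisons confirmatory. The Kaplan-Meier correction is small and matters only if the fallback is used.

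**What to change.** 1. **Hospital Course (definitions).** State that a death attributed to PE, MI or stroke on autopsy where available, on the death certificate or in the terminal medical record counts as a fatal VTE, MI or CVA event. The already blinded data collectors classify each death as thrombotic, non-thrombotic or undetermined.
2. **Analysis (reporting).** Report VTE, MI and CVA with and without the record-based fatal events, and give the number of undetermined deaths by arm. State how deaths enter the chi-square analysis.
3. **Analysis (fallback).** Where time-to-event methods are used for VTE, MI or CVA, report cumulative incidence with death as a competing event in place of Kaplan-Meier with deaths censored.
4. **Optional.** A supportive comparison of VTE, MI, CVA or death. Under the assumed rates, deaths number 78 × 0.10 = 7.8 to 78 × 0.20 = 15.6 per arm against 3.9 to 6.2 tested events, so it would be mostly all-cause death and add little to the mortality comparison.

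The cost is protocol and SAP wording plus a cause-of-death field, if the case form lacks one. Treatment, testing and sample size do not change. The downside is that attribution from records is less certain than imaging, which is why those events are shown separately.

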#### Clinical Follow-up

Patient follow-up and disposition will be at the discretion of the treating surgeon. For the purposes of this study, patients will be followed for a period of six months from the day of surgery. At the time of follow-up, patients will be assessed for the incidence of complication including VTE, MI, CVA, wound complication, and all-cause mortality. If patients are not able to return to clinic, they (or their legally authorized representative) will be contacted by phone.

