## Safety Monitoring

## Statistical Considerations

### Randomization and Blinding

Subjects will be randomized into one of two study groups: TXA administration (treatment) or placebo (control). Subjects will be assigned to either the treatment group or control group using a pre-generated blocked randomization design. The randomization schedule will be developed by the study statistician and will be provided to Research pharmacy personnel who will make the study group assignment. Medications

will then be delivered to the emergency department in packaging that does not delineate whether it contains placebo or tranexamic acid. Thus, the patient, treating surgeon, emergency department physician, residents, hospitalist group, anesthesiologist, and data collectors will remain blinded to the treatment assignment.

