### Analysis

The primary outcome will be the proportion of patients transfused at least 1 unit of packed red blood cells during hospital admission. Secondary outcomes will include mean number of units transfused per patient, calculated blood loss, and incidence of adverse events at six months including: VTE, MI, CVA, wound complications, and all-cause mortality as previously defined. The cohort of patients treated with early administration of TXA in the ED will be compared to a control group who were not treated with TXA at any point. All outcomes will be reported descriptively using appropriate summary statistics, including 95% confidence intervals, where appropriate. Baseline variables, including fracture type, surgical procedure, presenting hemoglobin, history of coronary artery disease, American Society of Anesthesiologists (ASA) score, length of surgery, length of anesthesia and type of anesthesia will be summarized overall and separately by study group; because this is a prospective, randomized trial, no formal between-group comparisons of baseline covariates will be performed. Adverse events as well as the primary and secondary outcomes occurring during the hospital stay and up to six months following surgery will be evaluated using chi-square tests and logistic regression (for categorical variables) if complete follow-up is obtained for the study subjects. If follow-up varies because of subject withdrawal or lack of response at 6 months, these outcomes will be estimated and evaluated using survivorship methods such as Kaplan-Meier estimation and Cox proportional hazards regression. Two-sample t-tests will be used to compare continuous variables between the study groups. All statistical tests will be two-sided and the threshold of statistical significance will be set at  $\alpha = 0.05$ .

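### Six-month follow-up is tied to surgery although study drug starts earlier in the ED: unoperated patients have no window and the Kaplan-Meier/Cox fallback has no time zero

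*Combined protocol and SAP*

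**What the plan says.** **Follow-up and outcome windows.** Clinical Follow-up states that "patients will be followed for a period of six months from the day of surgery". Secondary Outcomes uses the same anchor for VTE ("Incidence of symptomatic VTE diagnosed within 6 months of surgery"), and for MI, CVA and wound complications. The mortality line gives six months but no starting point.

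**Start of treatment.** Initial Patient Encounter starts study drug well before that anchor: "After consent is obtained, treatment will be initiated in the emergency room with study medication obtained by ED pharmacy". The regimen is described as "TXA will be administered intravenously via bolus dose of 1g over ten minutes and an additional 1g over the subsequent 8 hours", and "Neither group will receive perioperative bolus dosing of TXA". Under Operative Course, medical clearance and stabilisation come before surgery.

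**Randomisation.** The schedule "will be provided to Research pharmacy personnel who will make the study group assignment", and the medication then goes to the emergency department. Assignment therefore precedes exposure.

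**Surveillance and analysis.** Hospital Course has patients evaluated for VTE, MI and CVA on every hospital day. The Analysis section refers to "Adverse events as well as the primary and secondary outcomes occurring during the hospital stay and up to six months following surgery". These outcomes are tested with chi-square and logistic regression if follow-up is complete. The switch to Kaplan-Meier and Cox is worded "If follow-up varies because of subject withdrawal or lack of response at 6 months". No time origin is given for those methods.

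**The concern.** The safety question is whether tranexamic acid given in the emergency department causes thrombotic events or deaths. The clock for answering it, as worded in Clinical Follow-up and Secondary Outcomes, starts at surgery, which comes after randomisation and after the start of drug. Two things are left open.

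1. **Patients without surgery.** Surgical treatment is an inclusion criterion, but it can be confirmed only after dosing in the emergency department. Someone who dies before the operation, or is never operated on, has been randomised and may have received drug, yet has no date from which to count six months.
2. **Time zero.** A survival analysis needs an origin. If surgery is used, an event before surgery has a negative time and a patient without surgery has no time at all. Dropping them would condition the comparison on reaching surgery, which happens after randomisation. If the origin is not fixed in advance, the analyst must choose it once the data exist.

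**Working it through.** **Plan's own figure.** The only calculated figure in the plan is the sample size for transfusion. With p1 = 0.50, p2 = 0.25, mean 0.375, two-sided alpha 0.05 and 80% power:

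n = [1.960 × √(2 × 0.375 × 0.625) + 0.842 × √(0.25 + 0.1875)]² / 0.25² = 57.7, so 58 per group.

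This reproduces the plan's figure (power at 58 is 80.2%). It does not involve the safety window, so the point leaves it unchanged.

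**Passages side by side**

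| Patient | Clinical Follow-up and Secondary Outcomes (from surgery) | Analysis section (hospital stay plus six months after surgery) |
|---|---|---|
| Event after surgery | Counted | Counted; origin of survival time not stated |
| In-hospital event before surgery, later operated on | Not clearly counted | Probably counted; negative time if surgery is the origin |
| Dies before surgery or never operated on | No window | Hospital stay covered; no six-month end date and no surgery origin |

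Randomisation is a date that every patient in the table has, and it precedes the drug.

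**Is the fallback likely to be used?** Its trigger is any withdrawal or non-response at six months. Assuming independent losses, the chance that all 156 patients are complete is 0.99^156 = 0.21 at 1% loss and 0.98^156 = 0.04 at 2% loss. Even light loss makes the fallback the more likely analysis.

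**How many events lie before surgery?** The documents give no inputs for this, so every line below is an assumption. Expected pre-operative events per arm = 78 × six-month incidence × share before surgery. At 3%, 5% and 10% incidence, an arm of 78 has 2.34, 3.90 and 7.80 events. With surgery d days after randomisation, the share is about (d/182.6)^k, where k = 1 is a constant hazard and k = 0.5 a front-loaded one.

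| Assumed share before surgery | 3% incidence | 5% | 10% |
|---|---|---|---|
| Constant hazard, 1–3 days: 0.5%–1.6% | 0.01–0.04 | 0.02–0.06 | 0.04–0.13 |
| Front-loaded (k = 0.5), 1–3 days: 7.4%–12.8% | 0.17–0.30 | 0.29–0.50 | 0.58–1.00 |
| Set directly at 5%–20% | 0.12–0.47 | 0.20–0.78 | 0.39–1.56 |

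**How many patients would have no surgery date?** If 0.5% to 5% of those randomised are never operated on or die first (assumed), that is 0.005 × 156 = 0.8 to 0.05 × 156 = 7.8 patients.

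**What is lost at the far end?** Ending the window at six months from randomisation excludes the last d days after surgery. With a constant hazard h = −ln(0.95)/183 (5% incidence), the expected loss per arm is 78 × [exp(−h(183 − d)) − exp(−183h)] = 0.02 events for d = 1 and 0.06 for d = 3.

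**The case against.** The strongest reply is that the plan already captures the events in question. Hospital Course looks for them every hospital day, and the Analysis section counts the hospital stay as well as the six months after surgery. No section says that survival time starts at surgery. This largely stands. A reader might infer that early thrombotic events will be lost, or that the sections contradict one another, and the documents support neither. What they support is an outcome definition that is silent on pre-operative events, an undefined window for patients without surgery, and an unstated origin.

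Other objections also have force:

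- **Mortality.** Its outcome line is not tied to surgery; only the general follow-up sentence is. For death the gap is a missing origin, not a wrong one.
- **Attrition.** A reader might take the planned attrition of at least 15% (about 23 of 156) as six-month loss, compute 0.85^156, about 1 in 10^11, and call the fallback certain. The Sample Size section does not say what kind of loss it means, and it is inflating a sample size for an in-hospital outcome. The trigger wording makes the fallback likely without that figure.
- **Early share.** A 5%–20% pre-operative share presumes that risk is concentrated early. Under a constant hazard the number of events is roughly a tenth as large.
- **Population.** Changing the origin does not by itself settle whether an unoperated patient belongs in the analysis, given the surgical inclusion criterion. The fix has to say so.
- **Contact date.** Bringing the six-month contact forward would cut short the wound window, which rightly runs from surgery. The contact should not move.

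**Conclusion.** The point holds as a minor, inexpensive improvement to the secondary safety outcomes. It rests on the text: a surgery anchor for follow-up and for VTE, MI and CVA, drug started earlier, no window for randomised patients who do not reach surgery, and no time zero for the fallback. Randomisation is the better origin because every patient has it, it precedes exposure, and it preserves the randomised comparison.

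The size cannot be established from the documents. Under the assumptions shown, pre-operative events range from about 0.01 to 1.6 per arm, and about 1 to 8 of 156 patients would lack a surgery date. A few patients at most is a fair expectation. The primary outcome and the sample size are unaffected, and nothing here shows that the safety comparison would be materially biased.

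**What to change.** - In **Secondary Outcomes** and **Analysis**, count VTE, MI, CVA and all-cause mortality over six months from randomisation in all randomised patients, operated on or not. Use randomisation as time zero for any Kaplan-Meier or Cox analysis.
- State that the surgical-treatment inclusion criterion does not remove a patient from this safety analysis after randomisation.
- Keep **wound complications** counted from surgery.
- In **Clinical Follow-up**, keep the contact at six months after surgery, which covers both windows. For patients never operated on, set it at six months after randomisation.

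Merely adding that in-hospital pre-operative events count would not be enough, because patients without surgery would still have no end date.

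The cost is a few sentences and one contact for each never-operated patient, which Clinical Follow-up already allows by phone. In-hospital surveillance needs no change.
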